# 2. AMENDMENT HISTORY

List details of all protocol amendments here whenever a new version of the protocol is produced.

2.0			
	11.05.15	[name]	Insertion of text to Section 5, Study design, page 8, following peer review.
3.0	02.09.15	[name]	Following provisional opinion from REC: Removal of all reference to Stage-1:Pre-Pilot.
3.0	02.09.15	[name]	Following provisional opinion from REC:  Amendments to flow chart (page 24) and patient contrast questionnaire (page 25).
3.0	02.09.15	[name]	Following provisional opinion from REC:  Amendments to 9.1, Serious Adverse Effects.
4.0	24.02.16	[name]	Change of trial coordinator
4.0	24.02.16	[name]	Change of contrast agent and risk profile
4.0	24.02.16	[name]	Contact name changes on PIS and consent form.
4.0	24.02.16	[name]	In accordance with trust policy an additional question has been added to the patient contrast questionnaire
	3.0 3.0 4.0 4.0 4.0	3.0 02.09.15  3.0 02.09.15  4.0 24.02.16  4.0 24.02.16	3.0 02.09.15 [name]  3.0 02.09.15 [name]  3.0 02.09.15 [name]  4.0 24.02.16 [name]  4.0 24.02.16 [name]  4.0 24.02.16 [name]

CONTEND Study Version number: 4.0 Version date: 24.0216

# 4. ABBREVIATIONS

CBU	Cambridge Breast Unit (including Cambridge Breast Cancer Research Unit)
CESM	Contrast Enhanced Spectral Mammography
CRF	Case Report Form
СТ	Computed Tomography
GP	General Practitioner
GCP	Good Clinical Practice
ID	Identification
LCC	Left cranio-caudal view
LMLO	Left medio-lateral oblique view
MDT	Multi-disciplinary Team Meeting
MRI	Magnetic Resonance Imaging
NICE	National Institute for Health and Care Excellence
NRES	National Research Ethics Service
RCC	Right cranio-caudal view
REC	Research Ethics Committee
RMLO	Right medio-lateral oblique view
ROC	Receiver Operating Characteristic
SAE	Serious Adverse Event

## 5.

# STUDY SYNOPSIS **Study Title** An assessment of the impact of **CONT**rast **EN**hance**D** Spectral Mammography (CESM) on patient management and comparison with MRI (CONTEND Study) Internal ref. no. RADIOL/2015/CONTEND **Study Design** The aim of this pilot study is to establish the Contrast Enhanced Spectral Mammography (CESM) technique and study procedures. Results of this pilot and feedback from staff will inform Phase 2 of the study which will be a larger, multi-centre, randomised control trial. The study will be undertaken by members of the Cambridge Breast Unit (CBU) at Addenbrooke's Hospital, Cambridge using CESM technology provided by GE Healthcare as an upgrade to the GE Senographe Essential digital mammography system. This technology is already established throughout the world and has FDA approval and is CE marked. This will be a randomised, sequential cohort study. Following standard mammography and ultrasound all women with lesions of suspicion 3, 4 or 5 will be randomised to either receive CESM in addition to their assessment procedure or to receive usual care. Sealed envelopes will be held at CBU reception desk containing either 'CESM' or 'Usual Care' and one will be selected at random to determine to which arm of the study the woman is allocated. After providing informed consent, those women randomised to receive CESM will undergo the procedure either during the same clinic visit or on a day following the initial clinic visit. This will be dependent upon clinic time and staff availability and the woman's own preferences / circumstances. The index lesion and any additional disease detected by CESM will be biopsied as appropriate and results will be discussed at the multidisciplinary meeting (MDT). For those with biopsy confirmed disease a decision will be made at that meeting regarding conservation surgery, mastectomy or neo-adjuvant therapy. For those with benign disease

confirmed by core biopsy standard care will be followed.

MRI will be performed on appropriate women in line with standard practice. Additional disease detected by MRI will be biopsied if this will influence patient management. Biopsies will be undertaken using either ultrasound or MRI guidance. These cases will be discussed at the MDT and a decision made regarding conservation surgery, mastectomy or neo-adjuvant therapy.

The pathway for women randomised to receive usual care will be the same as for those randomised to receive CESM, excluding the CESM procedure, i.e. they will undergo biopsy during their initial clinic visit and results will be discussed at the MDT where a decision regarding their future management will be made.

A flowchart illustrating patient pathways during the CONTEND Study can be found in Appendix I of this document.

A proforma will be used for each case to record patient pathway, results of biopsies and MDT patient management decisions.

Staff will be asked to provide feedback on patient acceptability and ease of undertaking the CESM procedure. They will also be asked to record any incidents of note, e.g. patient related problems; impact on clinic; issues with equipment. Time taken to undertake the examination will be recorded.

In order to compare the diagnostic accuracy of CESM with MRI, CESM images and MRI images will be anonymised and read by different readers - CESM images will be reported without the knowledge of the MRI results and vice versa. Mammography and ultrasound images will be available. A completed report on a proforma will be the basis for statistical analysis.

Histopathology data collected following surgery or from core biopsy if surgery is not undertaken and will be used as the gold standard for measurement of tumour size and extent of disease. If the patient is having primary drug therapy, tumour size will be determined from the mammogram.

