# **Study Participants**

Women attending CBU who have lesions of suspicion 3, 4 or 5 following routine mammography and ultrasound.

50 patients with successful CESM examinations will be required to establish the technique, study procedures and to provide sufficient data to inform further study. It is estimated, due to randomisation procedure, approximately 100 patients will need to be recruited in order to obtain this number.
Recruitment to the study is planned to run for 12 months or until sufficient number of participants has been accrued. The study will end once data analysis is complete.
To assess the impact the addition of CESM has on patient management.
To compare the sensitivity and specificity of CESM with MRI.
The detection of additional disease by CESM that changes patient management. Analysis will be undertaken to determine the impact of CESM on patient management decisions (actual or hypothetical). These will be extracted from details recorded on the proforma.
Secondary endpoints are the sensitivity and specificity of CESM and MRI on a per lesion basis – including comparison of the maximum dimension of the index tumour – as assessed by independent readers and compared with surgical histopathology.
The efficacy of each technique at detecting additional lesions and the number of false positives identified by each will also be determined. False positives will be confirmed through follow up at 6 months.
Analysis of results will inform further study, e.g. sample size and power calculations, and will include an assessment of clinical technique and study procedures from staff questionnaires.

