### Number of Subjects

We plan to include 100 subjects in this study – approximately 50 to receive CESM and 50 to receive usual care.

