# 8.4 Study Procedures

# Screening and enrolment

Patients who have been identified as suitable for the study will be approached at the routine post-biopsy consultation when their diagnosis and treatment plan is being discussed. At this meeting, patients will be given both written and verbal information about the study.

If a patient wishes to enter the study, their eligibility will be checked by a Research Radiographer or Research Nurse and signed informed consent will be obtained. The patient will then be randomised and if she is in the CESM arm an appointment will be arranged for the procedure.

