### 10. STATISTICS

## 10.1 The Number of Participants

There will be approximately 100 participants in order to provide 50 who will undergo CESM.

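### The stated envelope draw fixes no order of use and no allocation log is described, so a redrawn or pre-opened envelope could not be detected

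*Protocol*

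**What the plan says.** The allocation mechanism is described in one place, Section 5 (Study Design): "Sealed envelopes will be held at CBU reception desk containing either 'CESM' or 'Usual Care", and then "one will be selected at random to determine to which arm of the study the woman is allocated". The envelopes are sealed and the arm is named inside. Nothing is said about numbering, opacity, how many envelopes of each kind there are, who prepares them, who draws, or how the draw is recorded.

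Section 8.4 (Screening and enrolment) adds no mechanism. After the eligibility check and signed consent it says: "The patient will then be randomised and if she is in the CESM arm an appointment will be arranged for the procedure". Section 8.1 (Number of Subjects) expects "approximately 50 to receive CESM and 50 to receive usual care".

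The only record described for each case, in Section 5, is a proforma covering the patient's pathway, biopsy results and the multidisciplinary team's decisions. The draw is not on that list.

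**The concern.** Envelope schemes protect a trial by forcing an order: the next patient gets the next envelope, and a departure shows up as a gap or a mismatch in a log. The sentence in Section 5 takes that protection away, because any envelope in the pool is a legitimate choice. If one is opened, found unwelcome and put back or thrown away, the process that the protocol describes gives no means of noticing.

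The setting gives staff both knowledge and opportunity. They have the mammography and ultrasound findings before allocation. Under Section 8.4 the approach is made at the post-biopsy consultation, so the biopsy diagnosis is known too. Usual care differs by omitting a visible procedure ("The pathway for women randomised to receive usual care will be the same as for those randomised to receive CESM, excluding the CESM procedure"), and no sham is described. Someone who believed that a particular woman would gain from CESM could act on that belief.

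The primary endpoint in Section 8.2 is the finding of additional disease that alters management. Steering women with a high chance of such disease into the CESM arm would raise the apparent yield of CESM and distort any comparison of management impact between arms. Section 5 also says that the pilot is meant to establish procedures for a larger multi-centre randomised trial, and allocation is one of those procedures.

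**Working it through.** **1. The plan's own figure.** Section 10.1 says: "There will be approximately 100 participants in order to provide 50 who will undergo CESM". At 1:1, 100 × 1/2 = 50, so the figure reproduces. The point concerns procedure and disputes no number in the protocol.

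**2. The passages side by side.**

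- *Order of use.* Section 5 gives a free pick and Section 8.4 is silent. No sequence is fixed anywhere. Numbering the envelopes would not create one while any envelope may be chosen.
- *Record of the draw.* The Section 5 proforma, the case report form rules in Section 12.1 and the deviation reporting in Section 14 do not mention it.
- *Timing.* Section 5 describes the draw first and then says "After providing informed consent, those women randomised to receive CESM will undergo the procedure". Section 8.4 puts eligibility and consent before randomisation. The two do not agree on when an envelope may be opened. The Appendix I flowchart is not reproduced in the available text and is not relied on here.

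**3. Would arm totals reveal redrawing?** This is an illustration only. Assumptions: 100 women; each draw is an independent 50:50; for a share *f* of women (the targeted ones) staff redraw once if 'Usual Care' comes up. The protocol does not give the number, mix or replacement of envelopes.

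A targeted woman reaches CESM with probability 0.5 + 0.5 × 0.5 = 0.75. Overall, P(CESM) = (1 − f) × 0.5 + f × 0.75 = 0.5 + 0.25f.

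Expected targeted women are 100f × 0.75 in CESM and 100f × 0.25 in usual care. Each share is that count divided by the expected arm size. The last column is P(X ≤ 39 or X ≥ 61) for X ~ Binomial(100, P(CESM)).

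| f | P(CESM) | Targeted in CESM arm | Targeted in usual care | Split outside 40–60 |
|---|---|---|---|---|
| 0 | 0.500 | – | – | 3.5% |
| 10% | 0.525 | 7.5 of 52.5 (14%) | 2.5 of 47.5 (5%) | 5.9% |
| 20% | 0.550 | 15 of 55 (27%) | 5 of 45 (11%) | 13.5% |
| 30% | 0.575 | 22.5 of 57.5 (39%) | 7.5 of 42.5 (18%) | 27.3% |

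In each case targeted women are more than twice as concentrated in the CESM arm, while the arm totals usually look unremarkable. If instead the pool held 50 of each, unwanted envelopes were put back and all were eventually used, the totals would be 50:50 however much redrawing took place. A discarded envelope could be found only by counting against a known starting number, and none is stated.

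**The case against.** Four arguments on the other side carry weight.

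- *The envelopes are sealed.* This is a real safeguard, and it stands. Nobody can read the arm from the outside as the text is written. The exposure is redrawing or opening ahead, not seeing the label.
- *Silence is not absence.* A reader might infer that the envelopes are unnumbered and that no audit trail exists. The protocol says neither. Numbering, opacity and log sheets are often held in a separate working procedure, so the fair statement is that no log is described. The free pick is different: it is stated outright, and a log kept elsewhere would not give it an order.
- *The effect on results is less direct than it looks.* A reader might infer that steering would bias a planned test of management change between arms. No such test is stated. The synopsis words the primary endpoint as additional disease found by CESM, which can occur only in the CESM arm. Section 10.2 limits its analyses to patients with MRI, CESM and surgical histopathology. A between-arm contrast can be read into Section 8.2, which drops the reference to CESM, and into the hypothesis of an earlier decision in Section 7.1, but it is not settled. This stands, and it limits the consequence to the CESM arm's case mix and to any between-arm comparison that is made.
- *Unequal arms are not a defect.* A reader might object that balance is not assured. The protocol promises only an approximate split, and chance imbalance is a property of ordinary simple randomisation. That complaint is not made here.

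The pilot's small size and lack of stated power lower the severity. They do not remove the point, since establishing procedures is one of the pilot's aims.

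**Conclusion.** The concern holds in limited form. The protocol positively states a free draw from a pool at the clinic desk, no other section supplies an order of use, and no record of the draw is described. Following the text as written leaves allocation open to steering by staff who already know the findings, and the described process would not show it.

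The size of any bias cannot be bounded from the documents, and nothing in them suggests that steering is intended or likely. The figures above rest on assumed independent 50:50 draws and an assumed share of redraws. They show only that arm totals are a poor detector. What is at risk is the case mix of the CESM arm, any comparison of management impact between arms, and the soundness of the procedure handed to the larger trial. The CESM–MRI accuracy comparison is made within patients and is not subject to between-arm imbalance.

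This should be corrected. It is not a critical fault.

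**What to change.** Replace the envelope sentence in Section 5 with a stated sequence:

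- Sequentially numbered, opaque, sealed envelopes are prepared from a pre-generated random list by someone not involved in recruitment.
- Envelopes are opened strictly in order, and only after eligibility and consent have been recorded.
- Each opening is logged with envelope number, participant ID, date and time, and the person who opened it.

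Then align Section 5 with the order already in Section 8.4, so that both place consent before randomisation, and check the Appendix I flowchart against it.

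The cost is a few hours to prepare the list, envelopes and log sheet, plus finding someone outside recruitment to do it. Sample size, endpoints and clinical care do not change.

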The purpose of this study is to refine the CESM technique, assess acceptability of the test and recruitment levels, establish study procedures and examine effect of CESM on patient management decisions. We also hope to demonstrate an increase in sensitivity and specificity compared to MRI. Analysis of results will inform further study, including power calculations. On completion of this project we intend to apply to the UK NIHR Health Technology Assessment Programme for funding to undertake a multicentre trial comparing the diagnostic accuracy of CESM with MRI (perhaps with an extension to CESM DBT if this technique becomes available and minimally proven in terms of clinical performance and workflow).

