### **Analysis**

Analysis will be undertaken to determine the impact of CESM on patient management decisions (actual or hypothetical). These will be extracted from details recorded on the proforma.

We will also compare the sensitivity and specificity of CESM and MRI on a per lesion basis - including comparison of the maximum dimension of the index tumour - as assessed by independent readers and compared with surgical histopathology.

Analysis of results will also be undertaken in order to inform further study, e.g. sample size and power calculations, and will include an assessment of clinical technique and study procedures from staff questionnaires.

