### 8.4.1 Informed Consent

Eligible patients for this study will be identified in the out-patient clinic by members of the breast team. Patients will be given written and verbal information about the study. Consent will be taken by experienced Research Radiographer or Research Nurse. Following their CESM imaging, patients will return to normal standard of care. Safety reporting requirements will end 72 hours after the procedure.

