# **CONTEND** study

# Patient contrast questionnaire

Affix	patient	ΙD	label	here
	patient	ייו	label	11010

As part of the Contrast Enhanced Spectral Mammography (CESM) procedure, we are seeking your permission to administer an injection of contrast medium (dye) as part of your examination.

We need to ask you the following questions prior to your injection:		
Have you had injections of contrast medium in any past examinations in x-ray?	Yes	No
If yes, did you have any problems related to this injection?	Yes	No
If yes, please state:	1	
Are you allergic to anything?	Yes	No
If yes, please state:		
Do you have asthma?	Yes	No
Are you diabetic?	Yes	No
If you are diabetic, do you take metformin?	Yes	No
Do you have an overactive thyroid? (hyperthyroidism)	Yes	No
Are you on interleukin 2 therapy?	Yes	No
Do you suffer from sickle cell anaemia?	Yes	No
Do you suffer from Chronic Kidney Disease (CKD)?	Yes	No

Do you suffer from any brain pathology? Tumour, epilepsy, seizures?				Yes	No
If yes, are you currently taking any	med	ication for this? Ple	ease state:	Yes	No
Please state the date of the first da	ay of y	your last menstrua	I period:		
Please state the date of the first da	ay of y	your last menstrua	<del>l period:</del>		
Is there any chance you might be p	oregn	ant?		Yes	No
Do you use oral contraceptive pill?				Yes	No
Do you take hormone replacement	thera	apy (HRT)?		Yes	No
Please do not sign this form unt	il you	ı are with the rad	iographer.		
Print name		Signature		Date	
For official use only					
Date of blood test: eGF		R: Serum creatinine:			
Practitioner		Signature		Date	

CONTEND Study	Version number: 4.0	Version date: 24.0216

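### Acceptability of CESM is a purpose of the pilot, but only staff report it, and the withdrawal rule drops the women most likely to find CESM unacceptable

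*Protocol*

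**What the plan says.** The Rationale (Protocol, section 6) sets out what the pilot is for: "The purpose of this study is to refine the CESM technique, assess acceptability of the test and recruitment levels, establish study procedures". It adds that the results will feed the planning of a multicentre trial.

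The synopsis (section 5, Study Design) says how acceptability will be learned: "Staff will be asked to provide feedback on patient acceptability and ease of undertaking the CESM procedure". Staff are also to note incidents, including problems related to the patient, and the duration of each examination.

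The Analysis paragraph of section 8.4 says that the work to inform further study "will include an assessment of clinical technique and study procedures from staff questionnaires". That sentence, and its counterpart in the synopsis, concern technique and procedures. Neither mentions acceptability.

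The one form that patients complete is in Appendix II. Its lead-in is "We need to ask you the following questions prior to your injection", and its items cover contrast history, allergy, comorbidity, medication and pregnancy.

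Under the subject withdrawal criteria in section 8.1, a woman who reacts badly to the contrast or the procedure, or who cannot finish it for any reason, is withdrawn. Data on withdrawn women are left out of the analysis. Section 9.3 adds that bruising and allergic reactions to contrast will not be recorded for the study.

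**The concern.** Whether a test is acceptable to patients is a question about their experience. The plan puts it to the people who carry out the test. They can judge workflow and ease of use well, but they can only infer how a woman felt about the injection, the compression and the added examination, and whether she would agree to it again.

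The withdrawal rule adds a second problem, because exclusion depends on the outcome of interest. A woman who felt unwell or stopped early is the one whose view most affects an acceptability estimate, and she is the one removed.

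At stake is a pilot deliverable. The Rationale also argues that same-day CESM should lessen anxiety, and nothing named in the protocol would let the pilot check that with the women. The information cannot be recovered later: a rating not taken at the visit is lost, and no analysis plan can supply it.

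**Working it through.** **Step 1. The plan's own figure.** Sections 5, 8.1 and 10.1 give about 100 participants so that 50 have CESM, split about equally. Required total = CESM examinations / allocation share = 50 / 0.5 = 100. The stated figure reproduces. Section 5 specifies 50 *successful* examinations, so any failures come on top of the 50.

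**Step 2. Purpose against data source.**

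| Item | What the protocol provides | Who answers |
|---|---|---|
| Acceptability of the test (section 6, purpose) | Feedback on patient acceptability (section 5) | Staff |
| Technique and study procedures | Staff questionnaires (sections 5 and 8.4) | Staff |
| Safety before contrast | Questionnaire (Appendix II) | Patient, before the injection |
| Incidents and examination time | Staff record (section 5) | Staff |

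The only row answered by the patient comes before the test and so cannot describe her experience of it. Self-reported acceptability ratings named in the protocol: 0 of about 50.

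**Step 3. What the withdrawal rule removes.** The protocol gives no failure rate, so the number of failures f is an assumption. With 50 successes, the share of attempted examinations that drops out is f / (50 + f):

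- f = 1: 1/51 = 2.0%
- f = 3: 3/53 = 5.7%
- f = 5: 5/55 = 9.1%
- f = 8: 8/58 = 13.8%

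**Step 4. Bounding the distortion.** Take the extreme case in which all 50 completers find CESM acceptable and none of the failures does. The analysed set shows 50/50 = 100%. Among all attempted the figure is 50 / (50 + f): 98.0%, 94.3%, 90.9% and 86.2% for f = 1, 3, 5 and 8. In this scenario the overstatement equals the share removed in Step 3. If some completers are dissatisfied, or some failures have nothing to do with how the test was experienced, the gap is smaller.

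**The case against.** The strongest defence is that nothing is misstated. The synopsis openly says that staff will report on acceptability. The Rationale speaks of acceptability of the test and promises no patient-reported measure. Acceptability is not among the objectives (section 7) or the endpoints (section 8.2), and no progression rule rests on it. Staff also note patient-related problems, so difficult visits need not go unseen. The staff questionnaire is not shown, so staff may in practice ask women for their views. The withdrawal rule covers data held on subjects, and a staff member's general impression might not count as such.

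Most of this stands, and it limits the weight of the point. It does not remove it. An incident note captures notable events and not each woman's view. Any question that staff put to women would still be relayed second-hand. If staff feedback on withdrawn women is meant to be kept, the protocol does not say so. It is not an objection to the plan that staff know which women had CESM, because acceptability is not compared between arms.

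A reader might go further and infer that recruitment levels are also measured in the wrong people, because section 8.4 says "If a patient wishes to enter the study, their eligibility will be checked by a Research Radiographer or Research Nurse". The document does not support that:

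- The same section opens with "Patients who have been identified as suitable for the study will be approached at the routine post-biopsy consultation", and section 8.4.1 says "Eligible patients for this study will be identified in the out-patient clinic by members of the breast team". Identification therefore precedes the approach, and the later check is confirmatory.
- Willingness to consent is itself an inclusion criterion (section 8.3.2), so full eligibility could not be settled before a woman is asked.
- Recruitment levels can be read as accrual, which is measurable: 100 / 12 = about 8.3 a month at target.
- Assumed uptakes of 80% (125 approached) and 25% (400 approached) both yield 100 women at this centre. They differ only when carried over to centres with a different throughput.

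No tally of women approached or declining is described, but a screening log is a routine record that may sit in a document not shown.

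**Conclusion.** The point holds for acceptability only. A stated purpose of the pilot is served by a proxy source, no patient-completed measure is named, and the withdrawal rule takes out the women whose experience is most informative. The resulting statement would be a staff impression leaning towards completers.

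In size, none of about 50 women is due to give her own rating, and for 1 to 8 assumed failures 2.0% to 13.8% of attempted examinations leave the analysed data. The failure counts are illustrative. The bias reaches those percentages only if every completer is satisfied and every failure is not.

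The primary endpoint does not use acceptability data, so gaps in those data do not affect it. This is an inexpensive improvement to a secondary deliverable and not a flaw in the trial's main question. The recruitment reading should not be raised as an error.

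**What to change.** 1. **Section 5, Study Design (and the matching text in section 8.4).** Have every woman who attends for CESM, including those who do not complete it, fill in a short card at the end of the visit on discomfort, anxiety and willingness to have the test again. Name this as the acceptability measure. Keep staff feedback for ease of use and workflow. Record whether the examination was completed and, if not, at what point and why it ended, so that failures unrelated to the woman's experience can be told apart.
2. **Section 8.1, subject withdrawal criteria.** State that acceptability and completion data from women who have ill-effects or do not finish CESM stay in the analysis, unless the woman withdraws consent for use of her data. Report acceptability among all who attended, with completers shown separately. This changes only which data are analysed, not when the procedure is stopped.
3. **Optional.** An anonymous tally of women approached and declining would let uptake be reported beside accrual.

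Cost: a one-page card, about two minutes per woman having CESM, and a minor amendment needing ethics committee approval. Randomisation, imaging and care are unchanged.

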# 8.2 Primary and Secondary Endpoints/Outcome Measures

The primary endpoint is the detection of additional disease that changes patient management. Analysis will be undertaken to determine the impact of CESM on patient management decisions (actual or hypothetical). These will be extracted from details recorded on the proforma.

Secondary endpoints are the sensitivity and specificity of CESM and MRI on a per lesion basis - including comparison of the maximum dimension of the index tumour - as assessed by independent readers and compared with surgical histopathology. The efficacy of each technique at detecting additional lesions and the number of false positives identified by each will also be determined.

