### 8.3.3 Exclusion Criteria

The presence of any of the following will preclude patient inclusion:

- Known or suspected pregnancy
- Breast implant
- Previous breast cancer
- Known renal impairment
- History of anaphylactoid or anaphylactic reaction to any contrast media

- Contrast media within 24 hours prior to CESM
- Commencement of neo-adjavant chemotherapy, hormone treatment, radiotherapy or surgery for this episode

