# 10.2 Analysis of Endpoints

Data from all eligible subjects will be included in the analyses. These will be patients for whom we have data from MRI, CESM and surgical histopathology.

Statistical significance of differences between CESM and MRI will be calculated using McNemar's test . Receiver operating characteristic (ROC) curves will be constructed for both imaging modalities.

Agreement between maximum lesion diameter based on CESM and MRI or CESM and histopathology will be expressed in Bland-Altman plots.

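### For women given drug therapy between imaging and surgery, post-treatment histology stays the reference for additional lesions and extent, so a true lesion that treatment clears can be counted as a false positive

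*Protocol*

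**What the plan says.** **Reference standard.** Section 5 (Study Design) makes histopathology of the surgical specimen the reference, with this alternative: "core biopsy if surgery is not undertaken and will be used as the gold standard for measurement of tumour size and extent of disease". The next sentence gives the only exception: "If the patient is having primary drug therapy, tumour size will be determined from the mammogram".

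**Per-lesion accuracy.** Section 8.2 defines sensitivity and specificity of CESM and MRI per lesion, "as assessed by independent readers and compared with surgical histopathology". The endpoint text in Section 5 and the Analysis paragraph of Section 8.4 say the same. None of the three makes an exception for drug therapy. Section 7.2 lists additional lesions, contralateral lesions, total extent and false positives among the analyses.

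**Who is included.** After imaging and biopsy, "a decision will be made at that meeting regarding conservation surgery, mastectomy or neo-adjuvant therapy" (Section 5). Section 8.3.3 excludes only women with "Commencement of neo-adjavant chemotherapy, hormone treatment, radiotherapy or surgery for this episode". Section 10.2 defines the analysed women: "These will be patients for whom we have data from MRI, CESM and surgical histopathology".

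**What else is known about each lesion.** For CESM, "The index lesion and any additional disease detected by CESM will be biopsied as appropriate". For MRI, "Additional disease detected by MRI will be biopsied if this will influence patient management". Section 5 has biopsy results entered on the proforma and has false positives confirmed by follow-up at 6 months.

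**The concern.** The exception for tumour size makes sense only if tissue removed after drug therapy no longer represents the disease that was imaged. The same reasoning applies to whether an additional focus was there and how far disease extended, but the exception stops at size.

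At stake are secondary measures: false-positive counts, specificity and total extent. The effect need not be equal for the two tests, because the one that finds more true foci has more to lose when foci vanish before the reference is taken. Sections 5 and 8.4 say the results will inform sample size and power for later work, so an error here could be carried forward.

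**Working it through.** The protocol gives no figure for this group, so there is nothing to reproduce. The check has two parts.

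**1. Following one woman through the text.** She has a suspicious lesion and no treatment yet, so Section 8.3.3 does not exclude her. CESM and MRI each show a second focus. The multidisciplinary meeting chooses neo-adjuvant therapy, and surgery follows.

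- Section 10.2: she has CESM, MRI and surgical histology, so she is analysed.
- Section 5: surgery was undertaken, so core biopsy is not her reference. Tumour size comes from the mammogram; extent does not.
- Section 8.2: the second focus is compared with surgical histology.
- If the focus is gone, no malignant lesion matches the finding, and both tests can be charged with a false positive.
- If some of the focus remains, the detection still counts as correct, but total extent is understated and both tests appear to overestimate it.
- The 6-month follow-up does not help. A focus removed by treatment would be absent then too, and the error would seem confirmed.
- If a pre-treatment core was positive, the result is on the proforma, but no text lets it outrank later surgical histology.

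**2. Illustrative size.** From the protocol: 50 women with CESM (Section 10.1), and sensitivity for additional cancers of 56% (CESM) and 88% (MRI) in the 52-patient comparison cited in Section 6. Assumptions not in the protocol: all 50 also have MRI; 10–30% have drug therapy and then surgery; 0.2–0.4 additional malignant lesions per woman; 10–50% of those gone at surgery; no credit for pre-treatment biopsy.

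Lesions lost = 50 × share treated × lesions per woman × share gone. Spurious false positives = lesions lost × sensitivity.

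| Case | Lesions lost | CESM | MRI |
|---|---|---|---|
| Low | 50 × 0.10 × 0.2 × 0.10 = 0.1 | 0.1 × 0.56 = 0.06 | 0.1 × 0.88 = 0.09 |
| Middle | 50 × 0.20 × 0.4 × 0.25 = 1.0 | 0.56 | 0.88 |
| High | 50 × 0.30 × 0.4 × 0.50 = 3.0 | 1.68 | 2.64 |

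The chance that at least one lesion is lost, 1 − (1 − lesions lost / 50)^50, is 0.10, 0.64 and 0.95 in the three cases.

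The cited study had 2 CESM and 13 MRI false positives. The middle case is 0.56 / 2 = 28% of the first and 0.88 / 13 = 7% of the second. The high case is 84% and 20%.

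Fifty women with both tests is an upper bound, since Sections 5 and 6 say MRI is used selectively. If 15 to 25 women qualify (assumption), the range is multiplied by 0.3 to 0.5: CESM 0.06 × 0.3 = 0.02 up to 1.68 × 0.5 = 0.84, and MRI 0.09 × 0.3 = 0.03 up to 2.64 × 0.5 = 1.32.

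**Sensitivity.** In the middle case there are 50 × 0.20 × 0.4 = 4.0 additional cancers in treated women. CESM finds 2.24 and MRI 3.52. If a quarter vanish whether detected or not, 3.0 remain, of which CESM found 1.68 and MRI 2.64. The ratios are 1.68 / 3.0 = 56% and 2.64 / 3.0 = 88%, unchanged in expectation.

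**The case against.** The strongest reply is that the protocol has no rule scoring a vanished lesion as a false positive. The order of surgery above core biopsy is stated for tumour size and extent, not for lesion presence; additional findings are often biopsied before treatment; and settling a positive core against later histology is detail that a statistical analysis plan could hold.

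Part of this stands. The false-positive scoring is inferred from the reference standard, so the right statement is that such lesions can be misclassified, not that they will be. Pre-treatment biopsy would shrink the problem if it were allowed to count. But the reference for per-lesion accuracy is itself fixed in Section 8.2 as surgical histopathology, without qualification. An analysis plan that let a core decide would depart from that text, so the gap belongs to the protocol.

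A reader might also infer that every accuracy measure is distorted. The documents do not support that. Detected and missed foci drop out in the same proportion unless disappearance depends on detectability, about which the protocol says nothing, so expected sensitivity does not move.

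Nor does the primary endpoint move: it concerns additional disease that changes management, and those decisions precede the therapy. Women who never have surgery are also unaffected, because Section 10.2 leaves them out of the comparison.

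Finally, a reader might set the spurious false positives only against the cited CESM count of 2 and conclude that the effect is large. Against the MRI count of 13 it is modest, and the difference between the tests in the high case is 2.64 − 1.68 = 0.96 of a lesion.

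**Conclusion.** The point holds in a limited form. The protocol corrects the reference for tumour size in women treated before surgery and leaves additional lesions and extent tied to post-treatment histology. A true focus that disappears completely can be counted against the test that found it, and nothing else in the protocol would reveal the error.

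The expected number is between almost none and two or three lesions per modality. That range rests on assumed treatment, lesion and disappearance rates, on all 50 CESM women also having MRI, and on no use of pre-treatment biopsies; relaxing either of the last two lowers it. In a pilot of this size even one lesion is visible in a CESM false-positive count that may be near 2. The change is worth making because it is cheap, not because the trial's main conclusion depends on it.

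**What to change.** Add to Section 5 (reference standard) and Section 8.2, for women who receive drug therapy after imaging and before surgery:

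- A core biopsy result obtained before treatment, where one exists, is the reference for the presence of that lesion and outranks later surgical histology.
- A lesion not biopsied before treatment and absent at surgery is recorded as unverified and counted for each modality. Accuracy is calculated twice: with these lesions excluded, and with them as false positives.
- Total extent against surgical histology is reported without these women, because a core can prove presence but cannot measure extent.
- Accuracy is shown with and without these women.

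The cost is a few sentences and one more lesion category on the proforma; the biopsy results are already recorded there and no extra biopsy is needed. The downside is that a few lesions leave the main denominators. Because MRI findings are biopsied only when management would change, the unverified group may fall unequally on the two tests, and excluding it alone could flatter MRI. That is why both calculations should be shown.
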